Hypothesis 2C: *Staff will spend approximately 2 hours/participant in exercise supervision and coordination. Staff will report that level of supervision and time commitment was appropriate and feasible.* Staff time spent in exercise supervision will be calculated by [hours spent supervising exercise / number of individuals supervised simultaneously + hours spent scheduling and/or coordinating]. Staff's qualitative assessment of feasibility will be collected via narrative report.

Specific Aim 3:

Hypothesis 3A: *HIIT induces positive right ventricular and pulmonary vascular remodeling, improving right ventricular performance and exertional cardiac output, reflected by decreased glycolytic metabolites on peripheral venous metabolomics; improved exertional pulmonary artery systolic pressure on TTE; and improved oxygen pulse, ventilatory efficiency, and dead space fraction on CPET. Additionally, markers of left ventricular diastolic function on TTE will improve reflecting general positive training adaptations of HIIT.*(8) Metabolomics heat maps, partial least squares discriminant analysis, and t-test or ANOVA will be performed to compare pre- vs post-exercise training glycolytic metabolites. Pulmonary artery systolic pressure on TTE and oxygen pulse, ventilatory efficiency, and dead space fraction on CPET will be analyzed using descriptive statistics and compared pre- and post-exercise program by t-test. Resting left ventricular diastolic function (E/e') will be analyzed using descriptive statistics and compared pre- and post-exercise training by t-test.

Hypothesis 3B: *HIIT improves VO2max among patients with deployment-related respiratory disease.* VO2max will be analyzed using descriptive statistics and compared pre- and post-exercise training by t-test.

Hypothesis 3C: *HIIT improves dyspnea and health-related quality of life (SF-36).* SF-36 pre- and post-exercise training will be analyzed using descriptive statistics and compared pre- and post-exercise training by t-test.

Results will be analyzed according to an intention-to-treat protocol. A p-value of <0.05 will be used to establish statistical significance. Statistical analysis will be performed using SAS v 9.4 (SAS Institute Inc., Cary, NC, USA). For metabolomics data, the MetaboAnalyst 4.0 package will be used for analysis and XY graphs will be created using GraphPad Prism 8 (GraphPad Software Inc., La Jolla, CA, United States).

Sample Size: Based on published data in patients with asthma,(17) who represent the most similar disease phenotype undergoing HIIT interventions reported in the current literature, a sample size of 10 is anticipated to provide 90% power to detect a difference in VO₂max of 2 ml/kg/min after HIIT, assuming a standard deviation of 1.8 ml/kg/min at an alpha = 0.05 and up to a 10% dropout rate. For the purpose of this pilot study, a sample size of 12 is anticipated to yield sufficient preliminary data regarding cardiac and pulmonary vascular abnormalities and safety, feasibility and efficacy of HIIT in the described patient population with the intent of future analysis in a larger study.

F. Summarize Knowledge to be Gained:

This study will generate hypotheses of pulmonary vascular and cardiovascular contributions to exercise intolerance after airborne hazards exposure, particularly among patients who currently remain undiagnosed with traditional evaluation. Additionally, it will demonstrate safety and feasibility of HIIT in this population and generate preliminary data regarding its efficacy in improving cardiopulmonary performance and symptoms of exercise intolerance. **The results will 1) inform larger investigations of extrapulmonary mechanisms of post-deployment dyspnea, particularly pulmonary vascular and cardiovascular abnormalities and 2) provide justification for a randomized controlled trial of different exercise modalities' efficacy in improving exertional dyspnea after airborne hazards exposure.**

G. Funding:

This study will be supported by the Department of Veterans Affairs Airborne Hazards and Burn Pits Center of Excellence (AHPCE) Pilot Project Program Award #FY2023-001 and a CTRC Microgrant. The contents do not represent the views of the AHPCE, U.S. Department of Veterans Affairs or the United States Government.

H. References:

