Exercise training and in particular high-intensity interval training (HIIT) improves maximal oxygen uptake (VO₂max) among healthy individuals and those with pulmonary disease.^(7, 15) ^(16, 17) Fitness gains from HIIT may derive from changes in metabolic and protein expression contributing to muscle adaptation as well as cardiovascular adaptations including increased left ventricular compliance and right ventricular remodeling.^(2, 8, 18, 19) For example, in rats the shift to glycolytic metabolism which accompanies pathologic right ventricular remodeling in pulmonary hypertension is attenuated by HIIT,^(2, 3) and pulmonary vascular remodeling and right ventricular function improves after HIIT.^(2, 20) However, whether HIIT improves symptoms or functional capacity in deployment-related respiratory disease has not been investigated. Moreover, given uncertainties regarding mechanisms of deployment-related respiratory disease, recommendations on management of this syndrome in general are lacking.⁽²¹⁾ Therefore, the **primary objectives of this study are: 1) generate hypotheses regarding the role of cardiac and pulmonary vascular abnormalities in contributing to exercise intolerance and 2) generate pilot data regarding the safety, feasibility, and efficacy of HIIT in improving functional capacity and alleviating symptoms in deployment-related respiratory disease.** The results will inform a larger investigation of extrapulmonary mechanisms of symptoms and exercise interventions in deployment-related respiratory disease.

III. Research Methods

A. Outcome Measures:

Primary Outcomes:

- VO₂max
- Health-related quality of life (SF-36)

Secondary Outcomes:

- Gas exchange (oxygen consumption [VO₂], carbon dioxide production [VCO₂] and minute ventilation to generate calculations of oxygen pulse [VO₂/HR], ventilatory efficiency [VE/VCO₂], and dead space fraction [estimated dead space / tidal volume])
- TTE parameters of cardiac function (right ventricular pulmonary artery systolic pressure, mid-cavity diameter, tricuspid annular plane systolic excursion, right ventricular longitudinal strain, left ventricular ejection fraction, transmural peak inflow velocity of early rapid diastolic filling / early diastolic mitral annular velocity [E/e'])
- Peripheral venous blood untargeted metabolomics
- Borg rating of perceived exertion (RPE)
- Participation (attendance at supervised exercise sessions and diary of home sessions)

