The proposed study is a single-arm clinical trial to generate pilot data regarding the safety, feasibility and efficacy of an exercise intervention. Participants will complete a baseline assessment (Visits 1A +/- 1B) at 0 weeks followed by up to 12 weeks of HIIT intervention followed by a repeat assessment (Visits 2A +/- 2B). An overview of the study protocol is provided in Figure 1.

Figure 1: Protocol Overview

Visits 1A/1B and 2A/2B: Visits 1A and 2A will be performed in the inpatient unit of the Clinical and Translational Research Center at the University of Colorado. Each visit will include administration of SF-36 questionnaire, spirometry, and a cardiopulmonary exercise test. Peripheral IV will be placed for the purpose of venous blood draws for complete blood count, ferritin and untargeted metabolomics analysis.(1) Radial arterial line will be placed for continuous blood pressure monitoring and measurement of arterial blood gas and lactate. Participants will be oriented to VO2max testing protocol. Baseline fitness will be assessed by questioning to determine step protocol. Once arterial line is in place, participants will complete a symptom-limited CPET on an upright stationary bicycle. Workload will begin at 0 Watts and increase every minute by 10-30 W (based upon pre-testing questioning) to achieve volitional exhaustion with maximum workload at 8-12 minutes.(22) Heart rate and rhythm, blood pressure, oxygen saturation, and gas exchange parameters (VO2, VCO2, and minute ventilation) will be continuously measured. Borg RPE, arterial blood gas and lactic acid will be measured at rest, every 4 minutes during exercise, and at peak exertion. Attainment of a high-quality VO2max will be determined based upon achieving one or more of the following: a plateau in VO2; attainment of predicted VO2max, work rate, or heart rate; respiratory exchange ratio >1.15, and Borg Scale rating 9-10 on a 0-10 scale.(6) Peripheral venous blood draw for untargeted metabolomics analysis will be repeated at peak exercise.

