HIIT exercise intervention: HIIT sessions will be administered at the outpatient University of Colorado Clinical and Translational Research Center through the Investigations in Metabolism, Aging, Gender and Exercise (IMAGE) Research Group exercise lab. HIIT intervention will include 3 weekly supervised sessions (10 minutes warm-up followed by 4 x 4-minute intervals [4 minutes at 90-95% peak heart rate followed by 3 minutes at 60-75% peak heart rate]).(7) HIIT sessions will be performed on an upright stationary bicycle. Additionally, participants will be requested to complete 3 40-minute sessions of moderate aerobic exercise each week (Borg rate of perceived exertion 12-14). Aerobic exercise may be performed using any exercise modality. During the first three weeks of the exercise program, the exercise prescription will be modified to facilitate orientation to the training program and physiologic adaptation. Specifically, the first session will be performed with one-on-one supervision from a research coordinator. The coordinator will assist with identifying appropriate an exercise workload based upon the baseline CPET. Subsequent sessions will be performed with ready availability of coordinators to ensure heart rate targets are achieved. The first week of the program HIIT sessions will be modified to include 1 x 4 minute intervals (with a 10-minute warm-up and 3-minute cool-down for a total of ~20 minutes exercise). The second week HIIT sessions will include 2 x 4 minute intervals (with a 10-minute warm-up and 6-minute cool-down for a total of ~30 minutes exercise). The third week HIIT sessions will include 3 x 4 minute intervals (with a 10-minute warm-up and 4-minute cool-down for a total of ~35 minutes exercise). During the first week participants will complete home sessions of 20 minutes aerobic exercise. During the second week participants will complete home sessions of 30 minutes aerobic exercise. During the third week participants will complete home sessions of 35 minutes aerobic exercise. Participation and adverse events will be recorded at supervised sessions and through a diary of home aerobic sessions including time, activity, heart rate at approximately half-way point of exercise, symptoms and adverse events. The exercise diary will be recorded via REDCap MyCap (mobile device application to capture participant reported outcomes) or on paper according to participant preference.

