Anticipated risks of HIIT training include fatigue, shortness of breath and leg discomfort, and participants will be counseled of these risks. Additionally, study team will closely monitor for adverse events through observation as well as participant report. Adverse events will include the following: minor – hypotension (BP < 90/60), lightheadedness, hypoxemia (SpO₂ <80% for >60 seconds),(24) chest pain, arrhythmia, or need to terminate exercise for another reason; major – major adverse cardiac event (stroke, myocardial infarction or cardiovascular death) or hospitalization. Exercise session will be terminated for any minor adverse event and PI and study safety monitor will be notified. Patient will be referred to Emergency Room if any member of the study team or the participant feel referral is indicated. Additionally, participant will be evaluated by PI prior to engaging in any future sessions. If further participation is felt to be of risk to the patient by either PI or the study’s safety monitor, then participation in study will be terminated. Major adverse events are not anticipated, but if any should occur patient will be transported immediately to the Emergency Room. HIIT has been studied in various populations including those with good health but sedentary lifestyle,(8) moderate to severe asthma,(17) and coronary artery disease,(25) and similar or identical HIIT regimens to that described in this protocol studies have demonstrated >80% compliance without attributable adverse events.(8, 25) Additionally, the study design includes an initial baseline assessment with symptom-limited CPET. If the initial CPET identifies safety concerns with completing the study exercise protocol, those concerns will be addressed prior to participant completing any further intervention. If unable to be addressed then the participant will be removed from the study. Therefore, the proposed protocol is anticipated to be safe for participants.

Home exercise: In addition to HIIT sessions described above, participants will perform three sessions / week of 40 minutes aerobic exercise at moderate intensity (Borg rate of perceived exertion 12-14). Home exercise will be prescribed to minimize the risk of confounding from

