paradoxical decrease in non-HIIT day physical activity (an effect described in the literature of exercise training interventions).(26) The home exercise program will include a three-week “phase-in” period as described in the protocol above. Participants will keep a diary of home exercise as described above in “Study Design and Research Methods” that includes a field for symptoms and adverse events. Study personnel will collect the diary at 4-week intervals and at that time will also question participant regarding any adverse events not reported through other means. Home exercise has been studied in populations including those with chronic lung disease and pulmonary arterial hypertension without significant attributable adverse effects.(27, 28) Additionally, as described above all participants will undergo baseline CPET and if risks to engaging in an exercise regimen are identified they will be addressed prior to any further intervention.

Risks to a pregnant woman, embryo or fetus: Due to physiologic changes of pregnancy which are anticipated to impact response to exercise training, pregnant women will be excluded from this study. Women of child-bearing age will complete a urine pregnancy test prior to testing during Visit 1. If the test is positive, the participant will be informed and removed from the study. Additionally, participants will be counseled to avoid pregnancy during the study and will be removed from the study should pregnancy occur.

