Feasibility of exercise training program: A three-week familiarization / physiologic adaptation period has been built into the HIIT program to maximize the likelihood of participants being able to successfully perform the exercise training program. However, there is still the possibility of individuals being unable to complete the full intended training program due to injury or other reasons. Successful completion of HIIT sessions (including meeting target heart rate) will be assessed by the study team at least every 4 weeks. If an individual demonstrates >3 sessions over a 4-week period in which they fail to meet the exercise prescription, a study team member will discuss with the participant barriers to meeting the exercise prescription and help identify ways to address those barriers as appropriate. If an individual develops an injury which prevents them from completing the prescribed exercise program, they will be transitioned to a continuous exercise training regimen if possible (i.e. substituting "light exercise" training sessions for HIIT sessions) until able to resume HIIT, at which time they will begin HIIT with a repeat three-week familiarization / physiologic adaptation period. If they are unable to complete continuous exercise training, they will discontinue exercise training until able to resume. Completion rates of HIIT and continuous exercise training will be assessed as part of the analysis of the study (Aim 2).

E. Data Analysis Plan:

Specific Aim 1:

Hypothesis 1A: Pulmonary vascular remodeling resulting from prior airborne hazards exposures increases exertional pulmonary arterial pressure and right ventricular afterload, resulting in compromised right ventricular exertional performance with abnormal oxygen pulse, ventilatory inefficiency and increased dead space fraction on CPET and increased pulmonary artery systolic pressure during exertion (relative to healthy population norms).(4) Oxygen pulse, ventilatory efficiency, and dead space fraction will be analyzed using descriptive statistics. Results will be presented in reference to healthy population norms (ATS/ACCP guidelines).(6) Pulmonary artery systolic pressure will be analyzed using descriptive statistics. Results will be presented in reference to healthy population norms (American Society of Echocardiography guidelines).(5)

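### Minor: home sessions are prescribed by minutes and Borg 12-14, but the listed diary fields omit a Borg rating, no analysis reports sessions done as prescribed, and Hypothesis 2B hours rest on session counts

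*Combined protocol and SAP*

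**What the plan says.** **Prescription.** Section III.C (HIIT exercise intervention) asks for three home sessions a week, in any modality, with 20, 30 and 35 minutes per session in weeks 1 to 3. Section III.D (Home exercise) gives the full dose as "40 minutes aerobic exercise at moderate intensity (Borg rate of perceived exertion 12-14".

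**Diary.** Section III.C describes a "diary of home aerobic sessions including time, activity, heart rate at approximately half-way point of exercise, symptoms and adverse events". Section III.D refers back to this description without adding a Borg item, and says "Study personnel will collect the diary at 4-week intervals".

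**Borg.** The secondary outcomes in III.A include "Borg rating of perceived exertion (RPE" without saying when it is taken. Collection is described only for the cardiopulmonary exercise test: "Borg RPE, arterial blood gas and lactic acid will be measured at rest, every 4 minutes during exercise, and at peak exertion". That section uses a 0-10 Borg scale to judge test quality.

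**Outcome and analysis.** III.A lists "Participation (attendance at supervised exercise sessions and diary of home sessions" and defines participant time commitment as the sum of hours exercising. Under Hypothesis 2A, a home session enters the attendance numerator if it is reported in the diary. The 80% criterion is examined separately for HIIT, light exercise and combined sessions. Under Hypothesis 2B, total hours are derived from the number of supervised and reported unsupervised sessions.

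**Checks on delivery.** Potential Scientific Problems (Feasibility of exercise training program) states: "Successful completion of HIIT sessions (including meeting target heart rate) will be assessed by the study team at least every 4 weeks". It also states: "Completion rates of HIIT and continuous exercise training will be assessed as part of the analysis of the study (Aim 2".

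**The concern.** The home prescription has two measurable parts, duration and perceived exertion. The diary description does not list the second, and it records the first under a label that is not defined as duration. The analysis then uses only the fact that a session was reported. As written, a short or very light session counts the same as one done as prescribed.

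What is at stake is the description of the intervention. The pilot is meant to inform a randomised trial of different exercise modalities, and that design would benefit from knowing how much moderate exercise was delivered alongside HIIT. HIIT sessions have recorded heart rate and a stated review against target. Home sessions have neither an intensity criterion nor a planned summary of dose. For Hypothesis 2B, hours built from session counts will be wrong whenever home sessions differ from the length credited to them.

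**Working it through.** **1. How many sessions are involved.** Inputs: three home and three supervised sessions a week, up to 12 weeks, up to 12 participants (III.B, III.C).

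- Home: 3 × 12 = 36. Supervised: 3 × 12 = 36. Home share: 36/72 = 50%.
- Diary entries at full participation: 12 × 36 = 432.

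These are maxima, because the programme lasts up to 12 weeks.

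**2. Prescribed, recorded and analysed, side by side.**

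- *Session done:* three a week are prescribed; a diary entry records each; the Hypothesis 2A attendance rate uses it. This chain is complete.
- *Minutes:* 20, 30, 35, then 40 are prescribed; the diary has a time field, not stated to be minutes exercised; the Hypothesis 2B rule refers to numbers of sessions and gives no minutes per session.
- *Intensity:* Borg 12-14 is prescribed; no Borg item is listed; mid-session heart rate is recorded, but no home heart-rate target is set and no analysis of that field is planned.

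**3. What the attendance rate can and cannot show.** If a participant reports all 36 home sessions, home attendance is 36/36 = 100%. For assumed shares meeting the prescription of 100%, 75% and 50%, the sessions done as prescribed would be 36, 27 and 18, and the attendance rate would be 100% each time. The shares are illustrative; the documents give none.

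**4. Hours under Hypothesis 2B.** The plan's own figure is about 4.5 hours a week. Over 12 weeks this is 4.5 × 12 = 54 h, which matches the 27 h supervised plus 27 h home allowed for in III.D (Subject compensation). For home sessions that implies 27 × 60/36 = 45 minutes each.

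A count gives hours only after a length is credited to each session:

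- Weekly schedule: 3 × (20 + 30 + 35) + 27 × 40 = 255 + 1,080 = 1,335 min = 22.25 h.
- Flat 40 minutes: 36 × 40/60 = 24 h.
- Planning allowance: 27 h.

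The same 36 sessions therefore give 22.25, 24 or 27 home hours, depending on a choice the plan does not state. Beyond that, each minute by which actual length differs on average from credited length moves the total by 36 × 1/60 = 0.6 h, or 0.6/12 = 0.05 h a week. Summing recorded minutes removes both sources of error, apart from reporting error.

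**The case against.** The strongest reply is that home exercise is a supporting component. Section III.D says it is there to limit confounding from reduced activity on non-HIIT days. HIIT is the intervention under test, and its delivery is checked. A looser check on a supporting component in a 12-person, single-arm pilot is defensible. This stands, and it is why the point is minor.

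Much of the dose may also be recoverable. Time is naturally read as duration, especially beside the III.A definition of hours exercising. Mid-session heart rate can be set against peak heart rate from the baseline test. The diary list opens with 'including', so a Borg field may exist unlisted. All of this is fair. Still, heart rate cannot show whether Borg 12-14 was met, since no home target is set, any modality is allowed and the peak comes from a cycle test. If the rating is already collected, one sentence settles that part, and only the missing summary remains.

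The planned completion rates for continuous training come closest to an answer. In context, continuous training is first the substitute for HIIT after injury, though the wording might extend to home sessions. The rule for contacting participants after more than three missed prescriptions in four weeks could be read the same way. Neither gives a minutes or intensity criterion for home sessions.

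Two stronger readings are tempting, but the documents support neither:

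- *The 80% feasibility criterion is invalid or would be falsely met.* Hypothesis 2A and III.A define participation as attendance and reported sessions, and the rate measures exactly that. The plan sets no threshold for sessions done as prescribed, so 80% cannot be applied to one.
- *The gap between 4.5 hours a week and the scheduled dose results from the diary gap.* HIIT at its stated approximate lengths (20, 30, 35, then 40 minutes) also totals 1,335 min. Full attendance is then 22.25 + 22.25 = 44.5 h, or 44.5/12 = 3.7 h a week on average, and 6 × 40 = 240 min = 4.0 h a week in weeks 4-12. The shortfall against 54 h comes from the 27 + 27 h allowance, and it is a separate point.

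**Conclusion.** The point holds as a minor, cheap improvement. For up to 36 of 72 sessions per participant, the plan prescribes minutes and Borg 12-14, lists no Borg item in the diary, and plans no report of how many sessions met the prescription. The count-based rule for Hypothesis 2B does not match the plan's own definition of participant time.

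This rests on reading the listed diary fields as substantially complete and on a full 12-week programme. The effect on results cannot be sized, because the documents do not say how often home sessions would fall short. The attendance rate, the separate HIIT rate and the VO2max and SF-36 analyses are unaffected. What would be lost is a description of the delivered home dose, and the session rating is the one part that could not be reconstructed afterwards.

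**What to change.** 1. Add a session Borg rating to the MyCap and paper diaries. Name the scale as 6-20, since 12-14 does not exist on the 0-10 scale used at the exercise test. Label the time field as minutes exercised.
2. Keep the Hypothesis 2A attendance rate and its 80% criterion unchanged. Beside it, report descriptively the proportion of reported home sessions that met both that week's minutes and Borg 12-14. Give mid-session heart rate as a percentage of baseline test peak as support.
3. Compute Hypothesis 2B home hours from recorded minutes, in line with III.A.

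**Cost.** One extra self-reported entry per home session (up to 36 per participant), a clearer label on an existing field and a few sentences of text, with no new visits or tests. The data remain self-reported, and the descriptive figure may look less favourable than the attendance rate beside it.

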HIIT intervention: Participants will perform 3 x ~40-minute sessions/week (10 minutes warm-up followed by 4 x 4-minute intervals [4 minutes at 90-95% peak heart rate followed by 3 minutes at 60-75% peak heart rate]) for up to 12 weeks with a three-week “phase-in” period as described in the protocol above.(7) Sessions will be supervised by a Basic Life Support-trained research assistant experienced in monitoring safety during exercise. Supervision will occur at a ratio of no more than 1 research assistant per 5 exercisers. Heart rate will be monitored throughout HIIT sessions using a Polar chest strap heart rate monitor (Polar Electro; Kempele, Finland). Heart rate data will be displayed and recorded during exercise via the Polar Flow application on the participant’s cell phone. Each participant will be assigned an anonymized account on the Polar Flow application to which the participant and the study team will have access information.

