Hypothesis 1B: Increased right ventricular afterload causes maladaptive right ventricular remodeling which is reflected by increased glycolytic metabolites (compared to a reference healthy population).(2, 3) Metabolomics partial least squares discriminant analysis and t-test or ANOVA will be performed. Exercise metabolomics data collected in a healthy population (COMIRB 21-4354) will be used as a reference.

Hypothesis 1C: Impaired right ventricular performance contributes to reduced maximum oxygen consumption (VO2max) relative to healthy population norms, dyspnea and impaired health-related quality of life. VO2max will be analyzed using descriptive statistics and presented in reference to healthy population norms (ATS/ACCP guidelines).(6) Dyspnea and health-related quality of life will be assessed by SF-36 with scores analyzed by descriptive statistics. Scores will be presented in

reference to disease population references.(34, 35) Linear mixed models will be used to assess the relationship between impaired right ventricular performance as measured by pulmonary artery systolic pressure and VO2max. Covariates including BMI, gender, age and type of deployment-related respiratory disease will be included.

Specific Aim 2:

Hypothesis 2A: *HIIT is safe and feasible among military personnel suffering from deployment-related respiratory disease, with $\geq 80\%$ participation in prescribed sessions.*(8) Attendance will be calculated as (number of supervised sessions attended + unsupervised sessions reported by exercise diary) / total number of supervised + unsupervised sessions. Feasibility will be based upon attendance of $>80\%$ of prescribed exercise sessions, with separate analyses for HIIT sessions, “light exercise” sessions, and combined sessions. Safety/acceptability will be based upon an absence of major adverse events attributable to the exercise training program and $<5\%$ minor adverse events (calculated as the number of adverse events divided by the total number of exercise sessions throughout the program) attributable to the exercise training program.

Hypothesis 2B: *Participants will spend approximately 4.5 hours/week engaged in this program and will report that participation was feasible.* Total hours spent in exercise program will be calculated based upon number of supervised sessions and reported unsupervised sessions. Qualitative assessment of feasibility will be collected via narrative report.

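### Two minor adverse events in the <5% safety criterion are defined by blood pressure and SpO2 readings, but heart rate is the only physiological measurement described for training sessions, so the criterion is biased toward being met

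*Combined protocol and SAP*

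**What the plan says.** **Event definitions.** Protocol Section III.D, HIIT intervention, lists the minor events as "minor – hypotension (BP < 90/60), lightheadedness, hypoxemia (SpO₂ <80% for >60 seconds"), followed by "chest pain, arrhythmia, or need to terminate exercise for another reason". Two of these are defined by instrument readings, and the second needs a reading sustained over time.

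**Decision rule.** Section III.E, Data Analysis Plan, Hypothesis 2A: "Safety/acceptability will be based upon an absence of major adverse events attributable to the exercise training program", together with fewer than 5% attributable "minor adverse events (calculated as the number of adverse events divided by the total number of exercise sessions throughout the program").

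**Measurement in training.** For HIIT sessions, Section III.D states: "Heart rate will be monitored throughout HIIT sessions using a Polar chest strap heart rate monitor". An assistant trained in basic life support supervises, with at most five exercisers per assistant, and the "study team will closely monitor for adverse events through observation as well as participant report". For home sessions, Section III.C describes a diary with time, activity, one heart rate near mid-session, symptoms and adverse events. Section III.D, Home exercise, adds questioning about adverse events when the diary is collected every 4 weeks.

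**Where blood pressure and SpO2 are measured.** Section III.C describes continuous recording of both during the cardiopulmonary exercise tests at Visits 1A and 2A. No such recording is described for a HIIT or home session.

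**The concern.** A rate is interpretable only if the events in the numerator could have been detected in the sessions that make up the denominator. For the two threshold events, the plan describes no means of detection in training other than symptoms or appearance. Non-detection can only lower the numerator, so the error runs in one direction.

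The pooled denominator adds to this. Half the planned sessions are home sessions of moderate exercise, in which a threshold event cannot be identified from the diary fields described. Including them dilutes any rate that belongs to the high-intensity sessions.

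At stake is the Aim 2 conclusion. The protocol says the study will demonstrate safety and that its results will justify a randomised trial. A reader of the final report would take a minor-event rate below 5% to include hypotension and hypoxemia as defined, when silent episodes had not been looked for. Section III.D also ties session termination and notification to any minor event, so for these two events that rule rests on the same undescribed readings.

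**Working it through.** **1. Ascertainment of each listed event in training, as written**

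| Minor event | Needs a reading? | Route described for training sessions |
|---|---|---|
| Blood pressure below 90/60 | Yes | None described; indirectly through symptoms |
| SpO2 below 80% for more than 60 s | Yes, sustained | None described; indirectly through symptoms |
| Lightheadedness, chest pain | No | Observation, report, diary, questioning |
| Stopping exercise for another reason | No | Observation, report, diary |
| Arrhythmia | Partly | Symptoms and heart rate; rhythm recording is described only for the exercise tests |

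The gap is therefore silent threshold events, with arrhythmia a borderline case.

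**2. The criterion in event counts**

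The 5% limit is a fixed threshold with no derivation to reproduce. Inputs from the protocol: up to 12 participants, up to 12 weeks, 3 supervised and 3 home sessions per week. I assume 12 participants and full adherence.

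- HIIT sessions: 12 × 12 × 3 = 432. 5% is 21.6, so 21 events pass (4.86%) and 22 fail (5.09%).
- All sessions: 12 × 12 × 6 = 864. 5% is 43.2, so 43 events pass (4.98%) and 44 fail (5.09%).

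**3. Size of the undercount**

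The documents give no event rates, so the silent-event rate r per HIIT session is an assumption, shown over a range. Missed events = 432 × r. The rate is understated by r on the HIIT denominator and by 432 × r / 864 = r/2 on the pooled one.

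| Assumed r | Missed events | Points on 432 | Points on 864 |
|---|---|---|---|
| 2% | 8.64, about 9 | 2 | 1.0 |
| 5% | 21.6, about 22 | 5 | 2.5 |
| 10% | 43.2, about 43 | 10 | 5.0 |

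The last column also isolates the dilution. Even if every threshold event were measured, a 10% rate confined to HIIT sessions would average to 5.0% over all sessions.

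**4. Effect on the chance of meeting a <5% limit**

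Illustration on the HIIT denominator, which separates non-detection from dilution. Assume detected symptomatic events in 2% of sessions, threshold events in a further r, and a share s of threshold events detected. Treat sessions as independent. Then P(pass) = P(X ≤ 21), with X binomial(432, 0.02 + r × s).

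| r (true rate) | s = 0 | s = 25% | s = 50% | s = 100% |
|---|---|---|---|---|
| 2% (4%) | 99.99% | 99.8% | 98.8% | 85.0% |
| 5% (7%) | 99.99% | 97.3% | 69.3% | 4.4% |
| 10% (12%) | 99.99% | 69.3% | 4.4% | <0.1% |

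Where the true rate is under 5%, non-detection changes little. Where it is above, the verdict depends mainly on how many threshold events are detected. Events would cluster within 12 participants, so these probabilities are sharper than they would be in practice; the direction is unaffected.

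**The case against.** The strongest case on the other side has five parts.

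- **Monitoring is more than the strap.** This stands. A reader might infer that training goes unmonitored apart from heart rate. The protocol does not support that: it provides supervision, observation, participant report, adverse-event recording at supervised sessions, diaries and periodic questioning. Symptomatic hypotension or hypoxemia would probably be counted, if only as lightheadedness or early stopping.
- **The text is silent, not contradictory.** Also correct. Blood pressure and SpO2 may be taken in practice, and a 60-second definition suggests that some measurement was intended. But the plan has to be read as written, and if readings are planned, stating so is simple.
- **The outcome is already defined as what is recorded or reported** (Section III.A). This helps, but it changes neither the threshold definitions nor the denominator. The separate HIIT and home analyses in Hypothesis 2A are stated for attendance, not for the safety rate.
- **The baseline exercise test screens participants**, with both variables measured to exhaustion and safety concerns addressed before training. This may make silent events rarer. It does not ascertain them over up to 36 HIIT sessions per participant.
- **This is a 12-person single-arm pilot**, only attributable events count, and the criterion also requires no attributable major event, with a safety monitor reviewing. All true, and it limits the consequences. It does not remove the bias in a rule the plan itself uses to conclude on safety.

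**Conclusion.** The point holds as a gap in ascertainment with a known direction: the <5% criterion is biased toward being met. It applies to threshold events without symptoms, not to minor events in general.

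The size is unknown. Over an assumed silent rate of 2% to 10% of HIIT sessions, the undercount is about 9 to 43 events, or 2 to 10 points on the HIIT denominator and 1.0 to 5.0 points on the pooled one. This rests on 12 participants, full adherence, threshold events confined to HIIT sessions, and all missed events being attributable.

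A reader might go further and infer that silent events would by themselves breach the limit. The documents do not support that. They give no rate, 10% is only the top of an assumed range, and 43 of 864 (4.98%) would still pass. Nor do they show that the programme is unsafe. Which monitoring is clinically right is not judged here.

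**What to change.** Reconcile the monitoring description and event list (Section III.D, HIIT intervention) with the safety criterion (Section III.E, Hypothesis 2A), so that each event in the criterion matches how it is ascertained.

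- **If blood pressure and SpO2 are not recorded in training:** state that the <5% criterion and the Aim 2 safety conclusion cover observed or reported events only. Report the minor-event rate separately for supervised HIIT sessions and home sessions, each on its own denominator, in place of one pooled rate.
- **If they are recorded:** say in which sessions, and use only those sessions as the denominator for the two threshold events.

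Readings from the exercise tests should not stand in for safety during training.

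The first route changes wording and tabulation only, with no new data collection; its cost is a narrower safety claim. The second, where readings are already taken, needs the sessions named and the denominators set accordingly.
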